## 2. Study Design

### 2.1 Overall design

Longitudinal retro and prospective , observational cohort study of up to 90 ApoE4-positive adults (age  $\geq 55$ ) followed for 24 months, with in-person visits every 6 months and continuous remote monitoring with Oura Ring and a subset of 10 subjects. No investigational drug or device is administered. Participants will undergo venous or capillary blood collection, CSF collection as part of this study are not performed, digital cognitive and speech biomarker assessments,( EEG, retinal imaging or MRIs may be performed outside of this study if ordered by referrals and shared by agreement with this study. Particularly in subjects that convert during this study.

Samples and data will be used to (a) apply and refine the Insilco-derived P&R model for conversion prediction, and (b) compare model-predicted risk with the study observed conversion events.

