## 2.2 Insilco and in vitro lead-in (pre-FIH phase)

[name] and [name] are currently conducting Insilco analyses using existing, independently collected cohorts that include whole-genome sequencing (for APOE and PRS), plasma proteomics including pTau217, imaging, and longitudinal cognitive/clinical outcomes. The data referenced here already have IRB approval and participant consent, and no additional contact with participants will take place during this phase.

The goal of the Insilco work is to develop and calibrate a proteogenomic Progression and Risk (P & R) model that estimates the short-term hazard of conversion from cognitively normal (CN) or very mildly impaired to pTau217-positive MCI due to AD. The model integrates:

- A polygenic risk score (PRS) for AD (APOE-excluded) plus APOE genotype.
- Plasma proteomic features selected from prior multi-omic studies of dementia and brain health.
- DNA methylation features associated with proteomic and cognitive/brain phenotypes.
- Key plasma AD biomarkers (pTau217, A $\beta$ 42/40, GFAP, NfL).
- Standardized Baseline cognitive and functional measures.

Model development and comparison

We will develop and compare at least two classes of time-to-event models:

1. A proteogenomic P & R model, which combines PRS + APOE with a parsimonious panel of plasma proteins including pTau217 and grounded with cognitive-functional tests.
2. A proteo-methyl-genomic model grounded with cognitive-functional tests.
3. A proteo-methyl-genomic - emr-lifestyle risk - oura ring data risk model, - grounded with cognitive-functional tests.

For each model, we will:

- Split source cohorts into training and internal validation sets or use cross-validation.
- Fit Cox proportional hazards or related survival models with time to conversion to MCI/AD or pTau217-positive MCI as the outcome.
- Derive a continuous risk score (linear predictor) and estimate discrimination (Harrell's C, AUC/ROC at fixed horizons such as 2–5 years) and calibration (calibration plots, Brier scores).
- Compare models using C-index/AUC and pragmatic criteria (assay cost, number of markers, ease of clinical implementation) to select a single P & R model for the FIH study.

Derivation of CN and SCD 4 risk groups and their expected transition event rates

Using the selected P & R model, we will apply the fitted risk equation to CN participants in the external cohorts and estimate their predicted near-term hazard of conversion. We will then:

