- Define 4 Categories CN individuals whose predicted 2–5-year conversion risk to MCI lies above a prespecified percentile cut-off (25 % lowest risk quartile, 25% next to lowest risk quartile, 25% next to highest risk quartile, and 25% highest risk quartile)
- Define 4 Categories of SCD whose predicted 2–5-year conversion risk to MCI lies above a prespecified percentile cut-off (25 % lowest risk quartile, 25% next to lowest risk quartile, 25% next to highest risk quartile, and 25% highest risk quartile)
- Estimate annual conversion rates within these model-defined groups (CN vs SCD), which are expected to differ by several-fold based on prior work showing strong stratification by proteomic, cognitive assessment, and multi-omic risk scores.

These estimated event rates (number of pTau217 positive MCI conversions per patient-years) are then used to justify the future FIH longitudinal sample size and follow-up duration described in Sections 1.2 and 3.2.

Fixed model for the FIH cohort

Once selected, the P & R model will be locked (fixed coefficients and included markers) before analysis of the FIH cohort. For each enrolled participant, we will calculate the P & R risk score at baseline and use it to:

- Assign CN participants to 4 CN Risk Levels and 4 SCD Risk Levels (per the thresholds derived above).
  - Generate individual predicted hazards of conversion for comparison with observed events (primary and secondary analyses).  
The FIH study itself is thus a prospective validation of a pre-specified P & R model developed entirely from existing data.
- 

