### **4.4 Biospecimen handling and storage.**

Informed consent	X						
Inclusion / exclusion criteria	X	X	X	X	X	X	X
Medical / neurological / psychiatric history	X						
Medication review	X	X	X	X	X	X	X
Physical and neurologic examination		X				X	O
Vital signs (clinic or wearable)	X	X	X	X	X	X	X
Documentation of prior ApoE genotype and WGS / array data	X						
PRS calculation & stratification (once data available)		X					

CDR (global and CDR-SB, no-informant version)		X	X	X	X	X	X
Digital cognitive battery and brief speech measures (Punto Health)		X	X	X	X	X	O
BIOFLUID COLLECTION (core)							
Venous or capillary blood (pTau217 + core panel for P&R model)		X	X	X	X	X	X
Additional plasma markers (extended AD panel, as budget permits)		O	O	O	O	O	O
Blood methylome / other discovery omics (sub-cohort only)		O	O	O	O	O	O

Clinical labs from EMR or PCP (CBC, CMP, etc.)	0	0	0	0	0	0	0
CSF collection (clinically indicated lumbar puncture only)		0					0
Resting / provoked EEG (sub-cohort, if available clinically)		0				0	0
Retinal hyperspectral imaging (if available clinically)		0				0	0
Amyloid PET (standard-of-care only, if ordered by clinician)		0	0	0	0	0	0
MRI / structural imaging (standard-of-care only)		0	0	0	0	0	0

Digital devices and monitoring							
Oura Ring data linkage / device confirmation	O	X					
Continuous Oura monitoring (sleep, activity, HR metrics)		X	X	X	X	X	X
Digital monitoring adherence check (Oura + cognitive app)		X	X	X	X	X	X
Risk score calculation and staging							
Calculate P&R risk score and risk level		X	X	X	X	X	X
Update CN / SCD / MCI Stage I status and event determination		X	X	X	X	X	X

† Triggered visits or remote assessments will occur when digital monitoring, participant report, or clinical assessment suggests possible cognitive decline or functional change; they may include focused cognitive testing and repeat blood sampling for key biomarkers (e.g., pTau217) and will prompt referral to a neurologist if criteria for MCI with positive biomarkers are met.

---

Notes:

- Total in-clinic visits: 5 required (Baseline + 4 follow-ups at 6, 12, 18, 24 months), plus optional triggered visits.
- Total biospecimen collections: 5 venipuncture/capillary sessions minimum (Baseline + 4 follow-ups), plus optional triggered samples

Duration of participation: 24 months from baseline with continuous remote monitoring

---

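### The P&R model lock is due only before analysis, and other sections let study data into the model, so the stated rule does not secure a pre-specified prospective validation

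*Protocol*

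**What the plan says.** Section 2.2 (fixed model for the FIH cohort) states that "the P & R model will be locked (fixed coefficients and included markers) before analysis of the FIH cohort". It continues: "For each enrolled participant, we will calculate the P & R risk score at baseline and use it to" assign risk levels and produce predicted hazards. The second use reads "Generate individual predicted hazards of conversion for comparison with observed events (primary and secondary analyses". The study is then described as a "prospective validation of a pre-specified P & R model developed entirely from existing data". The risk-level cut-offs come from the external cohorts.

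The schedule table printed under Section 4.4 has a row "Calculate P&R risk score and risk level", marked at baseline, at Months 6, 12, 18 and 24, and at triggered visits. The row for updating clinical status and determining events carries the same marks.

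Four other places bear on whether the model is fixed:

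- Section 2.1 says samples and data from the study will be used to "apply and refine the Insilco-derived P&R model for conversion prediction".
- The PRS definition, also in Section 2, standardises the raw score in an ancestry-matched reference population. Its example is an external dataset together with the first participants enrolled.
- Section 2.2 says "We will develop and compare at least two classes of time-to-event models" and then lists three. One is to be selected on C-index or AUC plus practical criteria. No date is given.
- Section 6.1 compares the AUC of proteogenomic and proteo-methylome-genomic models in this cohort. These are two of the listed candidates.

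**The concern.** Aim 1 is to validate a fixed model's discrimination at 24 months. That result is confirmatory in kind only if nothing in the score could respond to this cohort. A lock tied to analysis gives weaker protection than one tied to the first score, because outcome knowledge builds up from Month 6 onwards in a study where the same programme selects the model, scores participants and records conversions. If the model is settled or adjusted late, the AUC reported for Aim 1 is optimistic, and its confidence interval does not show this.

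The content of the lock is also narrow. Coefficients and markers fix the linear predictor only if its inputs are fixed too, and they do not by themselves yield a predicted hazard. Section 2 writes the hazard as a baseline hazard times the exponential of the linear predictor, and the lock sentence does not mention the baseline hazard.

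**Working it through.** The protocol gives no event rate, expected event count, target AUC or power, so there is no figure to reproduce. The values below marked as assumed are assumptions.

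**1. Order of events under the text.** Score: Month 0. Event determination: Months 0, 6, 12, 18, 24 and triggered visits. Lock: any time before analysis. A lock after the last Month 24 visit would satisfy the sentence, although every conversion would then be known.

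**2. Size of the selection effect if the choice came late.**

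- Inputs: N = 90 (Section 2.1) and 100 (Section 3.2); three candidates (Section 2.2).
- Assumed: 5, 10 or 20 events; true AUC 0.70 or 0.80, equal for all three; within-group correlation between scores 0.5 or 0.8.
- The event counts match assumed annual conversion of about 3%, 6% and 12%. With N = 90 over two years, 90 × (1 − e^(−0.06)) = 5.2, 90 × (1 − e^(−0.12)) = 10.2 and 90 × (1 − e^(−0.24)) = 19.2.
- Score model: μ·y + √ρ·c + √(1−ρ)·e, with μ = √2·z(AUC), c shared across candidates and e specific to each. There were 2,000 replicates per setting, and the largest of the three AUCs was kept.

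| Events | Mean rise in apparent AUC, best of 3 | Sampling SD of one AUC |
|---|---|---|
| 5 | 0.040 to 0.074 | 0.10 to 0.12 |
| 10 | 0.030 to 0.055 | 0.07 to 0.09 |
| 20 | 0.022 to 0.041 | 0.05 to 0.07 |

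Hand check: the expected maximum of three standard normals is 3/(2√π) = 0.846, so the rise is roughly 0.846 × SD × √(1−ρ). For 5 events, AUC 0.70 and ρ = 0.5 this is 0.846 × 0.119 × 0.707 = 0.071 (simulated 0.073). For 20 events, AUC 0.80 and ρ = 0.8 it is 0.846 × 0.055 × 0.447 = 0.021 (simulated 0.022). With one model locked before any event, this rise is zero.

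**3. PRS reference.** The standardised input is z = (raw − m)/s. If m and s come partly from participants, a fixed coefficient multiplies an input that changes with enrolment: m shifts predicted risk against the fixed cut-offs, and s rescales the PRS relative to the other markers. No outcome data enter here, so this is not outcome-driven optimism. It does mean that the score is not derived wholly from existing data.

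**4. Baseline hazard.** Suppose it were re-estimated in this cohort by the Breslow method, with rᵢ = exp(linear predictor) and dᵤ events at time u. Total expected events are Σᵢ rᵢ·H₀(tᵢ) = Σᵤ dᵤ·(Σ over those at risk of rᵢ)/(Σ over those at risk of rᵢ) = Σᵤ dᵤ, which is total observed. In simulation (assumed 3%, 6% and 12% a year, true slope 0.4 of the model's) the results were:

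- Re-estimated baseline: total observed/expected was 1.000000 in every data set.
- External baseline: about 2.0 to 2.1 when it was half the truth, 1.0 to 1.07 when right, and 0.50 to 0.53 when double.
- Re-estimated baseline, by risk level: 0.60 to 0.65 in the top quartile and 2.00 to 2.14 in the bottom half. A wrong slope therefore stays visible.
- AUC: unchanged, because the baseline hazard does not alter the ranking.

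**The case against.** The strongest reply is that the protocol's structure already points to an early choice. Selection sits in a lead-in that precedes the study, uses external cohorts, and yields a single model for it. P&R staging is applied in the inclusion criteria (Section 3.3), in baseline staging (Section 4.2) and in the baseline column of the schedule, so a model must exist at entry. The cut-offs are external. Section 6.1 calls the analyses mainly exploratory, and the selection effect is smaller than the sampling SD of a single AUC. Technical details of a lock can sit in an SAP, which is not at hand.

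Most of this stands, and it rules out three inferences that a reader might draw.

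- That the team intends to choose the model after seeing conversions. No passage says so, and staging at entry presumes a chosen model.
- That the baseline hazard will be re-estimated here, so that the predicted-versus-observed comparison passes by construction. No passage says so. The claim that the model is developed entirely from existing data points the other way, and re-estimation would force agreement only in total.
- That the risk-level cut-offs are open to this cohort. They are not.

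What the reply does not remove is that the protocol itself states the timing rule, and states it loosely. Nor does it remove the plan to refine the model or the early participants in the PRS reference. Those are conflicts within the protocol, not detail left to an SAP. The selection effect is smaller than the sampling error, but it runs in one direction and a confidence interval does not reflect it.

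**Conclusion.** The concern holds in limited form. The lock rule, read with the plan to refine in Section 2.1 and the PRS reference, does not secure a prospective validation of a pre-specified model. If selection among three equal candidates took place after events were known, the apparent AUC would rise by about 0.02 to 0.07. This rests on assumed values of 5 to 20 events, AUC 0.70 or 0.80 and correlation 0.5 or 0.8. The documents permit such a choice; they do not plan it.

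The baseline-hazard point is narrower. It is an unnamed component of the promised prediction. If it were taken from this cohort, calibration-in-the-large could not fail, but calibration by risk level would not be forced and Aim 1's AUC would not change.

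**What to change.** Three changes of wording:

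- **Section 2.2:** state that the full prediction equation is locked and dated before the first participant's baseline score is calculated, with none of it estimated from study participants. The equation comprises the coefficients, markers, PRS reference and normalisation constants, the externally derived 24-month baseline survival, and the externally derived cut-offs.
- **PRS definition:** drop early participants from the reference population, leaving the external ancestry-matched dataset.
- **Section 2.1:** reconcile the plan to refine with the fixed model. Label any refinement or recalibration in this cohort as secondary, and report it after the locked-model validation.

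The candidate comparison in Section 6.1 can stay, provided the model that carries Aim 1 is the one locked.

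The cost is protocol text and possibly a short delay, since baseline scoring may have to wait for the in-silico selection. Scoring the first ten participants later from stored samples would not avoid that wait, because Sections 3.3 and 4.2 and the schedule call for P&R staging at entry.

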### **3. Study Population**

#### **3.1 Target population**

ApoE4-positive adults aged  $\geq 55$  years, cognitively normal or with very mild cognitive changes (digital cognitive assessment equivalent of CDR 0–0.5), including a subset staged SCD/MCI/CDR  $< 0.5$  and pTau217 negative at baseline.

#### **3.2 Sample size**

The initial target is ten subjects starting with subjects that have Oura Rings and then expanding to one hundred total for the full 2-year study starting in September 'twenty-six. The targeted composition is:

- CN ApoE4 carriers with a range of polygenic risk scores (PRS): Initial target of three low PRS, 3 average PRS, 4 high PRS (later expanding to 33% in each category when the enrollment expands to a total of 100 subjects)
- Participants with MCI/CDR  $< 0.5$  and pTau217-positive at baseline will not continue enrollment in the study and will be referred to a Neurologist. These numbers may be adjusted if external sponsors join the project and support expanded enrollment. The size will be adjusted with more data on the annual CN to AD-MCI conversion rates from Insilco analyses and financial feasibility of intensive longitudinal assessments.

#### **3.3 Inclusion criteria**

- Age  $\geq 55$  years at enrollment.

- At least one ApoE4 allele documented by prior testing (e.g., prior genetic panel, research cohort genotyping, clinical ApoE testing).
- Whole-genome sequencing (WGS) data previously completed and participants willing to provide existing WGS data files (e.g., VCF, FASTQ, or equivalent) to the study team for polygenic risk score (PRS) calculation.
- If WGS is not available but targeted genotyping arrays covering AD risk loci are available, participants willing to provide these data for PRS calculation (the study will assess feasibility of array-based PRS on a case-by-case basis)
- 
- Cognitively normal or very mildly impaired at baseline, defined by:
  - The Ponto Test and digital cognitive assessment equivalent of a Global CDR 0 or 0.5, and no clinical diagnosis of dementia.
  - For CN and SCD, P&R model staging criteria will be applied (combining PRS, biomarker, and cognitive data).
- Subjects that do not currently qualify for MCI status. (ie with the equivalent of a g CDR 0.5 - 1.0 , and plasma or CSF pTau217 level above a validated cut-off for AD-MCI pathology.
- Ability to provide informed consent and to comply with study procedures.
- Willingness to wear/keep digital devices for continuous monitoring (e.g., smartphone app, wearable sensors, sleep device).
- Note on genetic testing: This protocol does not perform ApoE genotyping or whole-genome sequencing as a research procedure. Eligible participants must already have these tests completed through prior clinical care, prior research studies, or commercial/direct-to-consumer services, and must be willing to share the results and raw genomic data files with this study. Screening will confirm that (a) prior ApoE genotype shows at least one  $\epsilon 4$  allele, and (b) WGS or suitable array data exist and can be obtained for PRS calculation. Individuals without documented ApoE4 carrier status or without available genomic data for PRS are ineligible for this protocol.

### 3.4 Exclusion criteria

- Diagnosis of dementia (any cause) at baseline.
- Major neurological disorders that confound cognitive assessment (e.g., Parkinson's disease, stroke with residual deficits, epilepsy with frequent seizures).
- Major psychiatric illness (e.g., uncontrolled major depression, schizophrenia) that, in investigator judgment, interferes with participation or data interpretability.

- Uncontrolled systemic medical illness (e.g., unstable cardiac, hepatic, or renal disease) that may limit life expectancy to <3 years.
  - Use of investigational drugs or disease-modifying Alzheimer's therapies within 6 months prior to baseline that could confound biomarker trajectories.
  - Contraindications to EEG, retinal imaging, or MRI/PET (if clinically indicated), such as implanted incompatible devices or severe claustrophobia.
  - Inability or unwillingness to use required digital monitoring tools (e.g., no smartphone access, unwillingness to carry/wear devices, or severe hearing/vision impairment precluding their use).
  - Absence of prior ApoE genotype results or refusal to share existing ApoE/genomic data and EMR data with this study.
  - MCI pTau217 positive subjects will not continue to be enrolled in the study. They will be referred to a Neurologist.
- 

## **4. Study Procedures**

### **4.1 Schedule of events**

Each participant will have:

- Baseline visit (Month 0) with full assessments and biospecimen collection.
- pTau217 MCI positive subject will be referred to a Neurologist while the main CN group will have:

- Follow up visits on Months 6, 12, 18, and 24 ( $\pm 2$  months) with repeat biospecimens, neurocognitive testing, and safety review.
- Continuous or frequent digital monitoring (passive and active) throughout the 24 months. (or until they turn MCI positive)
- Optional "triggered" visits or remote assessments in response to signs of cognitive or functional decline detected by digital systems, participant report, or clinical assessment. (If blood biomarkers become positive then these subjects will be referred to a Neurologist and discharged from the study.

Total biospecimen collections per participant: 1 at baseline + 4 follow-ups = 5 (if they do not convert to MCI positive)

Biofluid: venipuncture and/or capillary collections every 6 months for 2 years.

### **4.2 Screening and baseline**

#### Screening (may coincide with baseline):

- Verification that participant has prior ApoE genotype results showing at least one ApoE4 allele (documentation from prior clinical or research testing required).
- Verification that the participant has prior whole-genome sequencing (WGS) data or equivalent high-density genotyping array data suitable for PRS calculation.
- Participants sign data release authorization allowing the study to obtain WGS/genomic data files from prior testing laboratory, research biobank, or direct-to-consumer service (if applicable).
- Optional Approval to Access past and /or future Oura Ring Data.
- Medical, neurologic, and psychiatric history; medication review.
- Physical and neurologic examination, including vital signs (partly collected from wearable device).
- Review of prior cognitive assessments, imaging, and biomarker results if available.

#### Baseline assessments:

- Cognitive and functional assessment: CDR (global and CDR-SB) and standard neuropsychological tests consistent with MCI trials (e.g., memory, executive function, language).
- Digital cognitive battery from Punto Health (or equivalent), including tasks sensitive to subtle CN → MCI transitions.
- Collection of blood (venous and/or fingerstick) for:
  - Plasma pTau217 and other AD plasma biomarkers (e.g., pTau181, Aβ42/40, GFAP, NfL).
  - Proteomic and methylome profiling per validated in vitro assays.
  - Clinical laboratory safety tests (e.g., CBC, CMP) if needed.
- Optional CSF collection (lumbar puncture) when clinically indicated (e.g., to resolve diagnostic uncertainty), analyzed for pTau217, amyloid, and other AD markers.
- EEG: resting EEG and a provoked EEG paradigm designed to probe memory and attention circuits (e.g., oddball or task-based paradigms).
- Retinal hyperspectral imaging to assay retinal signatures of amyloid and neurodegeneration were available.
- Amyloid PET scan if clinically indicated (per treating clinician) and standard-of-care in the setting; images/results will be captured for research use.
- Digital sensing initiation: participants receive and are trained on wearable devices and smartphone applications used to track smell (smell tests), location/mobility, activity, speech patterns, and sleep.

